### *Lipid Parameters*

Endpoint / Variables

 
• Observed and % change from baseline in lipid parameters by visit [total cholesterol, direct low-density lipoprotein cholesterol (LDL-C), high-density lipoprotein cholesterol (HDL-C)]
 

Planned Exploratory Displays

 
• Lipid parameter values for this study include total cholesterol, LDL-C (direct) and HDL-C. These values are collected according to the schedule outlined in the Schedule of Activities table (see Section 14.2.1). Lipid parameter values follow the derivation guidelines for laboratory values outlined in Section 14.6.4. The summaries described below will include summaries in both SI units and conventional units for each of the lipid parameters and will summarize log-transformed values.
 
• Total cholesterol, LDL-C (direct), and HDL-C values will be log-transformed and summarized using geometric mean, CV, minimum, P25, median, P75, and maximum for each scheduled visit by treatment group.
 
• Percent change from baseline in log-transformed total cholesterol, LDL-C (direct), and HDL-C on-treatment values will be summarized using geometric mean, 95% confidence interval, minimum, P25, median, P75, and maximum for each scheduled visit by treatment group.
 

### **8.3. Adverse Events Analyses**

Adverse events will be coded using the Medical Dictionary for Regulatory Activities (MedDRA) coding dictionary.

Adverse events analyses including the analysis of adverse events (AEs), Serious (SAEs) and other significant AEs will be based on GSK Core Data Standards. The details of the planned displays are provided in [Appendix 10: List of Data Displays](#).

For the purpose of AE summaries and analysis, the investigator-reported AE details will be used, regardless of the adjudication outcome of the event.

See Section 14.4.1 for AE treatment-state definitions.

The adverse event safety analyses will be based on the Safety population, unless otherwise specified.

### 8.3.1. Analysis of Adverse Event of Special Interest (AESI)

A prespecified list of MedDRA terms will be used to identify AESIs. Changes to the MedDRA dictionary may occur between the start of the study and the time of reporting and/or emerging data from ongoing studies may highlight additional AESIs, therefore the list of terms to be used for each event of interest and the specific events of interest will be based on the safety review team (SRT) agreements in place at the time of reporting. The details of the planned displays are provided in [Appendix 10: List of Data Displays](#).

AESIs are described in Section [14.6.4](#).

Summaries of AESIs will include the number, percentage, and rate per 100 person-years of subjects having at least one occurrence, the number of events, the number of subjects by number of occurrence, the characteristics of the AE (serious, drug-related, etc.), outcome, maximum intensity, time to first onset/worsening, and action taken summarized by treatment group. For each count, a subject will be summarized as follows:

- Serious/drug-related/severe/fatal: If any specific AE falls in the respective category, the subject will be counted in that category.
- Outcome: The subject will be counted within a category if there is at least one specific AE in that category.
- Maximum intensity: The specific AE with the maximum intensity will be counted for this purpose. For example, a subject will be counted in the ‘severe’ category if there is at least one specific AE with severe intensity. A subject will be counted in the ‘moderate’ category if there is at least one specific AE with moderate intensity and there is no specific AE with severe intensity.
- Time to first onset/worsening (days): The earliest of onset dates for the specific AE – treatment start + 1

If the AE onset date/AE worsening and/or resolution date is missing or incomplete in the database for any occurrence of the specific AE, time to first onset/worsening will be left missing for the subject. These summaries of special interest AEs will be provided for those AEs classified as treatment emergent, follow-up, and post-randomization.

The number and percentage of subjects reporting treatment emergent AESI will also be summarized by treatment group and by preferred term.

Cumulative incidence function (CIF) plots may be produced for each special interest AE summarizing the time to first occurrence of the special interest AE by treatment group, with the exception of the composite endpoint AESI (death, myocardial infarction, stroke, heart failure, thromboembolic events, thrombosis of vascular access). This endpoint will use a Kaplan-Meier plot. If there are less than 20 subjects total for both the daprodustat and rhEPO arm, then these plots will not be created. Competing risks for the AESI cumulative incidence plots include:

CONFIDENTIAL

204837

AE of Special Interest (Event of interest)	Competing Risk Events
Thrombosis and/or tissue ischemia secondary to excessive erythropoiesis	Death due to any cause prior to the AESI
Cardiomyopathy	Death due to any cause prior to the AESI
Pulmonary artery hypertension	Death due to any cause prior to the AESI
Cancer-related mortality and tumor progression and recurrence	All other non-cancer-related death prior to the AESI (use death date as the competing risk date)
Esophageal and gastric erosions	Death due to any cause prior to the AESI
Proliferative retinopathy, macular edema, choroidal neovascularization	Death due to any cause prior to the AESI
Exacerbation of rheumatoid arthritis	Death due to any cause prior to the AESI
Worsening of hypertension	Death due to any cause prior to the AESI

Dot plots displaying the incidence of the treatment emergent event will be provided for AESIs by AESI term and treatment group. The incidence rate in each treatment group and corresponding two-sided 95% confidence interval for the relative risk of the daprodustat group compared to the rhEPO group will be provided.

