9.2.3. Follow-up of AEs and SAEs

After the initial AE/SAE report, the investigator is required to proactively follow each participant at subsequent visits/contacts. All SAEs, and non-serious AEs of special interest (as defined in Section 9.2.7), will be followed until the event is resolved, stabilized, otherwise explained, or the participant is lost to follow-up (as defined in Section 8.3). Further information on follow-up procedures is given in [Appendix 3](#).

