Follow-up	
If AE onset date or AE worsening date is after the last non-zero dose date plus 1 day.  AE Start Date <math>></math> Last Non-Zero Dose Date + 1 day  AE Worsening Date <math>></math> Last Non-Zero Dose Date + 1 day  AE worsening during follow-up will be defined relative to the maximum intensity of AE prior to study treatment start date.
 
AE worsening date is the first date in the follow-up period, when AE intensity increased relative to the maximum intensity of the AE prior to study treatment start date.

Onset /Worsening Time Since 1 st Dose (Days)	
If Treatment Start Date <math>></math> AE Onset Date: AE Onset Date - Treatment Start Date  If Treatment Start Date <math>\leq</math> AE Onset Date: AE Onset Date - Treatment Start Date +1  If Treatment Start Date <math>></math> AE Worsening Date: AE Worsening Date - Treatment Start Date

CONFIDENTIAL

204837

Study Phase	Definition
	If Treatment Start Date $\leq$ AE Worsening Date: AE Worsening Date - Treatment Start Date + 1 Missing otherwise.
Onset/Worsening Time Since Last Dose (Days)	If Last Non-Zero Dose Date $\leq$ AE onset date: AE onset date – last non-zero dose date + 1 If Last Non-Zero Dose Date $>$ AE onset date: AE onset date – last non-zero dose date If Last Non-Zero Dose Date $\leq$ AE worsening date: AE worsening date – last non-zero dose date + 1 If Last Non-Zero Dose Date $>$ AE worsening date: AE worsening date – last non-zero dose date Missing otherwise.
Duration (Days)	AE Resolution Date – AE Onset Date/AE Worsening Date + 1
Drug-related	If relationship is marked 'YES' on eCRF or if the value is missing.

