**NOTES:**

- AEs that occur or worsen during interruptions of randomized study treatment will be classified as treatment emergent and post-randomization.
- If the last non-zero dose date is missing and the treatment start date is non-missing and the AE onset date or AE worsening date is on or after the treatment start date, then the AE will be considered to be treatment emergent.
- If AE onset date or AE worsening date is missing and AE resolution date is before the treatment start date, then the AE will be classified as Pre-treatment.
- If AE onset date or AE worsening date is missing and AE resolution date is either missing or on or after treatment start date, then the AE will be classified as treatment emergent and post-randomization.

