
 
• AE Patient Years: (Cumulative total of time to AE for subjects who have the AE + Cumulative total of censoring time for subjects without the AE) / 365.25 
 
○ For treatment emergent AEs, the start date of the patient years value for each subject should be the treatment start date.
 
 
 

CONFIDENTIAL

204837

Adverse Events

 
○ For post-randomization AEs, the start date of the patient years value for each subject should be the randomization date.
 
○ For follow-up AEs, the start date of the patient years value for each subject should be two days after the last non-zero dose date (last non-zero dose date + 2).
 

 
● Incidence Rate (per 100 patient years): <math>(100 * \text{Number of subjects with at least 1 AE}) / \text{AE person years}</math>
 

 
● For the analysis of the time to AE onset/worsening, if the AE onset/worsening date is missing then the time to AE onset/worsening will be counted as 1 day.
 

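### SAP 8.3.1 blanks time to first AESI onset when a resolution date is missing, although the formula does not use that date, and 14.6.4.3 treats a missing onset date differently

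*SAP*

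**What the plan says.** SAP 8.3.1 defines time to first onset/worsening as "The earliest of onset dates for the specific AE – treatment start + 1". A later sentence sets an exception. It begins "If the AE onset date/AE worsening and/or resolution date is missing or incomplete in the database for any occurrence of the specific AE" and ends "time to first onset/worsening will be left missing for the subject". No exemption is given for events still ongoing.

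SAP 14.6.4.3, in the general definitions for adverse events, has its own rule: "if the AE onset/worsening date is missing then the time to AE onset/worsening will be counted as 1 day". The same list builds AE patient-years from "Cumulative total of time to AE for subjects who have the AE" plus the censoring time of participants without the event.

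Three other places bear on the point:
- SAP 14.4.1.4 uses the resolution date to compute duration: "AE Resolution Date – AE Onset Date/AE Worsening Date + 1".
- Protocol 9.2.3 says that serious events and non-serious AESIs "will be followed until the event is resolved, stabilized, otherwise explained, or the participant is lost to follow-up".
- SAP 14.7.2.1 gives partial-date rules for concomitant medications and cardiovascular endpoints, but none for adverse events.

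**The concern.** The exception in 8.3.1 depends on a date that the quantity does not need. Follow-up of an AESI may end at stabilization, so AESIs with no resolution date are foreseeable. For those participants the onset date can be known and the onset time still left out. Because the condition applies to any occurrence, a later unresolved episode also removes a first onset that was fully documented. Whether a value is kept then depends on what happened after onset. If resolution differs between arms, the displayed onset times are no longer a like-for-like comparison.

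The second issue concerns missing onset dates. Section 8.3.1 leaves the time missing and 14.6.4.3 makes it 1 day. Section 8.3.1 places the rate per 100 person-years and the time to first onset in the same AESI summary. One table could therefore show no onset time for a participant whose person-time is counted as 1 day.

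What is at stake is how well the AESI characteristics tables describe timing: nine AESIs, each for the treatment-emergent, follow-up and post-randomization phases, which is 9 × 3 = 27 tables (3.053 to 3.079).

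**Working it through.** The plan states no figure on this point, so there is nothing to reproduce. The check applies both rules as written to hypothetical participants, with treatment starting on day 1.

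**Rules applied**
- 8.3.1: missing if any occurrence lacks an onset or a resolution date; otherwise the earliest onset day.
- 14.6.4.3: a missing onset counts as day 1; the earliest day is then taken.
- Corrected 8.3.1: missing only if an onset date is missing; otherwise the earliest onset day.

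| Hypothetical participant | 8.3.1 | 14.6.4.3 | Corrected 8.3.1 |
|---|---|---|---|
| One ongoing event, onset day 100 | missing | 100 | 100 |
| Resolved days 50–60, then ongoing from day 200 | missing | 50 | 50 |
| Onset missing, resolved day 120 | missing | 1 | missing, pending one convention |
| Resolved days 50–60, plus one occurrence with onset missing | missing | 1 | missing, pending one convention |

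Rows 1 and 2 isolate the resolution-date condition: a known onset of day 100 or day 50 is discarded. Rows 3 and 4 isolate the conflict over a missing onset, which removing the resolution-date condition does not settle.

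**How often a value would be lost.** Let q be the share of occurrences with no resolution date and k the number of occurrences per participant. Treating occurrences as independent, the chance of losing the value is 1 − (1 − q)^k. Both q and independence are assumptions; the documents supply neither.

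| q | k = 1 | k = 2 | k = 3 |
|---|---|---|---|
| 0.1 | 10% | 19% | 27% |
| 0.3 | 30% | 51% | 66% |
| 0.5 | 50% | 75% | 88% |
| 0.8 | 80% | 96% | 99% |

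For example, with q = 0.3 and k = 2: 1 − 0.7² = 0.51.

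**Does the text exempt ongoing events?** Section 8.3.1 does not. The notes to 14.4.1.4 speak of a missing resolution date without separating ongoing from unknown: "If AE onset date or AE worsening date is missing and AE resolution date is either missing or on or after treatment start date", the event is kept as treatment emergent. By contrast, the IV iron derivations in 14.6.3.2 name ongoing records explicitly. The literal reading of 8.3.1 is therefore that an unresolved event triggers the rule.

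**Scope of the two rules.** The 14.6.4.3 rule covers only a missing onset or worsening date. The 8.3.1 rule also covers an incomplete one. The SAP does not say which display each rule governs.

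**The case against.** A reader might infer that ongoing or chronic AESIs drop out of the safety analysis. The documents do not support that. Only the time-to-onset value is lost. The events remain in the counts, percentages, person-year rates, outcome, intensity and action-taken rows of the same tables, in the preferred-term table (3.080), in the dot plot and in the adverse event listing.

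A reader might also infer that the plan has nothing useful on when chronic AESIs begin. That goes too far. Cumulative incidence plots are listed for eight AESIs and a Kaplan-Meier plot for the composite, and the time and censoring definitions in 14.6.4.3 carry no resolution-date condition. This offsets the problem only in part. The cumulative incidence plots are optional, the plots are not made with fewer than 20 subjects across the arms, and those listed are treatment emergent only. For rare AESIs, and in the follow-up phase, the table is the planned summary of timing.

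The strongest textual objection is that SAP 14.7.2 describes missing data as requested items left blank, so a programmer could decide that an ongoing event has no missing resolution date. That reading is possible and would shrink the problem, but nothing in 8.3.1 states it.

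On missing onset dates, one can argue that a descriptive row may be left blank while a rate needs some time for every participant with an event. That would be a workable division if the SAP made it.

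Finally, the any-occurrence condition has a proper use for onset dates. If one occurrence has an unknown onset, the earliest known date may not be the first. That stands, and the fix respects it.

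**Conclusion.** The point holds in a limited form. The resolution-date condition in 8.3.1 serves no purpose for time to onset. Read literally, it selects the onset times shown in tables 3.053 to 3.079 towards resolved events. The conflict between 8.3.1 and 14.6.4.3 on a missing onset date is real but narrow.

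The effect is on descriptive safety displays. No hypothesis test, alpha level, event count or incidence is altered by the resolution-date condition. The missing-onset rule matters for rates only through the 1 day credited to the patient-years of each affected participant.

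The size of the loss cannot be taken from the documents. It might be tempting to put it at a third or a half of onset times, but no passage gives the share of AESIs that end without a resolution date. The percentages above only show how the loss would scale with an assumed share. The conclusion also rests on reading an ongoing event as one whose resolution date is missing, which the SAP neither states nor excludes.

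**What to change.** 1. In SAP 8.3.1, delete the reference to the resolution date, so that only a missing or incomplete onset or worsening date can affect time to first onset/worsening.
2. State one convention for missing and partial onset or worsening dates, and apply it in 8.3.1 and 14.6.4.3 to the AESI tables, rates and plots.
3. Keep the any-occurrence condition for missing onset dates unless that single convention replaces it.

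The cost is a few sentences in the SAP and a small change to the derivation, ideally before unblinding. No new data are needed.

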### **8.3.2. Adverse Events**

The number and percentage of subjects reporting at least one AE will be provided for each treatment group. These events will be summarized by treatment group, primary system organ class, and preferred term. Post-randomization, treatment emergent and follow-up AEs will be summarized separately.

Summaries of all treatment emergent AEs will be produced for the age group, gender, race group and weight quartile subgroups. Summaries of treatment emergent AEs by subgroup will be produced twice: by system organ class and preferred term and separately by overall frequency.

A listing of AE records for all subjects who reported AEs will be produced.

Summaries of all treatment emergent AEs will be provided by maximum intensity. For AEs reported more than once by a subject, the most severe intensity will be included in summaries where applicable. Analysis will be repeated for all drug-related treatment emergent AEs.

The number and percentage of subjects reporting the most common treatment emergent AEs (those occurring in  $\geq 5\%$  of subjects in any treatment group) will be summarized by preferred term and treatment group.

Additionally, the most common treatment emergent AEs will be summarized graphically by preferred term and treatment group. The incidence rate in each treatment group and corresponding two-sided 95% confidence interval for the appropriate comparator estimate (relative risk) of the daprodustat group compared to the rhEPO group will be provided. Displays will be sorted by magnitude of risk, from largest to smallest.

**CONFIDENTIAL**

204837

The number and percentage of subjects reporting treatment emergent AEs assessed by the investigator to be related to the study drug will be summarized by treatment group, primary system organ class, and preferred term and separately by overall frequency.

The number and percentage of subjects and the number of occurrences of common non-serious treatment emergent adverse events (those occurring in  $\geq 5\%$  of subjects in any treatment group) will be summarized by primary system organ class, preferred term, and treatment group and separately by overall frequency.

A listing of which subjects reported specific adverse events will be produced.

The hierarchical relationship between MedDRA SOCs, PTs, and verbatim text will be listed for all adverse events.

A listing of pre-treatment adverse events will be produced.

**8.3.3. Serious and Other Significant Adverse Events**

The number and percentage of subjects and the number of occurrences of SAEs will be provided for each treatment group. These events will be summarized by treatment group, primary system organ class, and preferred term. Pre-treatment, post-randomization, treatment emergent and follow-up SAEs will be summarized separately. Treatment emergent SAE preferred terms will also be summarized by treatment group and overall frequency.

A listing of reasons for considering as a SAE will be produced for all SAEs.

The number and percentage of subjects and the number of occurrences of treatment emergent drug-related SAEs, drug-related non-SAEs, fatal SAEs, non-fatal SAEs, and drug-related fatal SAEs will be summarized by treatment group: by primary system organ class and preferred term and separately by overall frequency.

A listing of fatal SAE records and a listing of non-fatal SAE records will be provided.

The number and percentage of subjects reporting treatment emergent SAEs will be summarized by treatment group, maximum intensity, primary system organ class, and preferred term.

The number and percentage of subjects reporting treatment emergent AEs leading to discontinuation of study treatment or withdrawal from the study will be summarized by treatment group, primary system organ class, and preferred term. Treatment emergent AEs leading to discontinuation of study treatment or withdrawal from the study will also be summarized by treatment group and overall frequency.

A listing of AEs leading to discontinuation of study treatment and a listing of AEs leading to withdrawal from study will be provided.

BP events and BP-related SAEs are defined in Section [14.6.4](#).

The number and percentage of subjects with at least one on-treatment BP event will be provided for each treatment group. In addition, this summary will include the number and percentage of subjects with at least one on-treatment BP event that is considered clinically significant and the number and percentage of subjects with at least one on-treatment BP event that is considered to be symptomatic.

The number and percentage of subjects reporting at least one treatment emergent BP-related SAE will be provided for each treatment group. In addition, the number of treatment emergent BP-related SAEs will be summarized by treatment group, primary system organ class, and preferred term.

A listing of other significant adverse events will be produced. Other significant adverse events are events that are not reported as fatal or serious but represent ICH-defined 'Other significant adverse events' (i.e., marked haematological and other laboratory abnormalities or led to an intervention, dose reduction, or significant additional concomitant therapy). For this study, other significant AEs will be defined as non-fatal non-serious AEs resulting in an action taken with study treatment of either 'dose interrupted/delayed' or 'dose reduced'.

#### **8.3.4. Other CV Events**

GSK has identified other CV events of interest for all clinical studies. In this study, investigators will be required to fill out the specific CV event page of the eCRF for the following CV AEs and SAEs or any event that may potentially be one of the categories listed:

- Arrhythmias
- Pulmonary hypertension (also an adverse event of special interest [AESI])
- Valvulopathy
- Revascularization

Electronically generated patient profiles for participants reporting these events will not be prospectively created.

#### **8.4. Clinical Laboratory Analyses**

Laboratory evaluations including the analyses of chemistry laboratory tests, hematology laboratory tests, and liver function tests will be based on GSK Core Data Standards. The details of the planned displays are in [Appendix 10: List of Data Displays](#).

Clinical chemistry, hematology and other laboratory tests are assessed in this study according to the schedule outlined in the Schedule of Activities table (see Section [14.2.1](#)) and include the following tests:

